2.5.3 Dose Rationale

2.5.3.1 AMG 596 Monotherapy

The predicted human PK parameters of AMG 596 were derived from previous clinical experiences with AMG 211, a BiTE[®] molecule for solid tumor indications that targets CD3 located on T-cells and carcinoembryonic antigen (CEA) located on cancer cells of solid tumors ([de Vries et al., 2015](#)). Given the similarities in protein structure, molecular weight, and solid tumor targets, the PK of AMG 596 was expected to be similar to AMG 211 ([AMG 211 Investigator's Brochure](#)). In addition, previous clinical experience with other BiTE[®] antibody molecules, including blinatumomab and AMG 110, have exemplified the consistency of pharmacokinetics across the BiTE[®] platform, with renal excretion expected to be the primary route of elimination (based on MW) and observed terminal half-lives ranging between 2.1-4.4 hours. For these reasons, the PK of AMG 596 is expected to be consistent with previous BiTE[®] antibody molecules clinically, with a predicted half-life of 2.9 hours. Clinical PK data for AMG 596 can be found in the [AMG 596 Investigator's Brochure](#).

The starting dose of AMG 596 was guided by the MABEL, an approach which has been safely used for previous BiTE[®] antibody molecules entering clinical testing.

AMG 596-mediated redirected lysis of EGFRvIII-transduced U-251 MG glioblastoma cells (U-251 MG/EGFRvIII) was identified as a sensitive parameter for AMG 596 MABEL determination. AMG 596-mediated redirected lysis by T cells from 20 different donors was analyzed and based on individual dose-response curves a mean (\pm SEM) EC₂₀ value of 0.07 ng/mL (\pm 0.004 ng/mL) was calculated and defined as in vitro MABEL of AMG 596. Using the assumptions of predicted human pharmacokinetics (PK) of AMG 596, a starting dose of \blacksquare μ g/day is predicted to achieve a serum C_{SS} of 0.088 ng/mL, which approximates EC₂₀ concentrations of AMG 596-mediated cell lysis.

Additionally, the predicted CSF steady state concentrations of AMG 596 at this dose are 0.66 pg/mL and 3.2 pg/mL assuming 0.75% and 3.6% CSF penetration, respectively,

relative to serum exposures. These estimates were based on literature reported CSF exposures with other protein therapeutics, including monoclonal antibodies and blinatumomab, a CD19-targeting BiTE[®] (Burstein et al., 2013; Klinger et al., 2016). Furthermore, the lower molecular weight of AMG 596 (relative to monoclonal antibodies) and the impairment of the blood brain barrier in glioblastoma patients (eg, due to resection of tumors in the brain) may result in increased CSF and/or brain penetration (Tabrizi et al., 2010). The selected start dose and dose escalation will aid in reducing number of dose escalation steps necessary to reach CSF concentrations associated with BiTE[®] activity, along with the use of single-subject cohorts and approx. 3-fold escalations in dose in the earlier cohorts.

The starting dose is supported by the nonclinical toxicology studies in cynomolgus monkeys. AMG 596 cross-reacts with cynomolgus CD3 and has been well-tolerated at doses up to ■ mg/kg/day, with no AMG 596-related adverse findings detected at this dose level. At the starting dose of ■ µg/day, the safety margins based on the observed C_{ss} were 13 400-fold before potency adjustment and 1910-fold after correction for a 7-fold difference in AMG 596 potency between human and cynomolgus monkey effector cells. Although cynomolgus monkeys do not express EGFRvIII, any EGFRvIII- or CD3-mediated events that may require dose management, including the elevation of cytokines, can be resolved quickly due to the predicted short half-life of AMG 596 and the interruption of the cIV regimen, which will allow timely washout of AMG 596.

Dose escalation decisions will be guided primarily by safety and tolerability to AMG 596 and intermediate dose levels may be proposed if necessary. These high doses may be necessary to achieve adequate tumor exposure of AMG 596 due to the specificity of EGFRvIII expression in glioblastomas and the natural barriers associated with brain penetration of various therapeutics. It is also for this reason however, that systemic adverse events related to the BiTE[®] mechanism of action (eg, cytokine release syndrome) are expected to be limited. Prophylactic treatment with corticosteroids and/or the implementation of step-dosing regimens can be used to mitigate further risk of adverse events from BiTE[®] activity. A pharmacodynamic drug interaction study showed that AMG 596-induced cytokine release could be reduced by dexamethasone, but dexamethasone might result in a reduced cytotoxic potency of AMG 596 when co-administered to patients.

At higher doses of AMG 596, there is a risk of potential acute renal dysfunction due to the inclusion of 9% sucrose in the IV formulation, an excipient common to many

IV formulations. Although this risk is mainly associated with the [REDACTED] µg/day doses (which results in > 1.8 g/week of sucrose), sucrose-induced acute renal dysfunction is typically temporary and resolves within 7-15 days, and markers of renal function will be monitored throughout the study. In addition, sucrose exposures at the highest dose in the study are expected to be lower than those achieved with several marketed IV-administered therapies (eg, infliximab, immune globulin intravenous), in which sucrose exposures of up to 26 g/week were observed.

Dose escalation in Group 2 subjects can start at the highest AMG 596 monotherapy dose deemed to be tolerated by DLRT for Group 1 subjects.

2.5.3.2 AMG 596 in Combination With AMG 404

No clinical safety information is available for the combination of AMG 596 with AMG 404. Based on biological mechanism of action and initial clinical safety information for monotherapies with AMG 596 and AMG 404, adverse events caused by synergistic activation of T cells are expected.

The first-in-human dose exploration and expansion study evaluating AMG 404 in subjects with advanced solid tumors is currently ongoing. Preliminary PK results of AMG 404 in 11 subjects with advanced solid tumors after AMG 404 administration as short-term IV infusions (approximately 0.5 hours) [REDACTED] were available for dose levels of [REDACTED] mg (3 subjects, first and second dosing intervals) and [REDACTED] mg (8 subjects, first dosing interval). The nonclinical pharmacology findings and preliminary human PK results from the FIH study provide increased confidence towards achieving an efficacious dose with doses planned in the study and results were consistent with those for other therapeutic anti-PD-1 mAbs. Moreover, no dose-limiting toxicities (DLTs) were observed in any of the 12 subjects who have received AMG 404 doses up to [REDACTED] mg [REDACTED]. Treatment-emergent adverse events were reported in 9 subjects (75.0%); the most frequently reported adverse events (≥ 3 subjects) were fatigue (4 subjects, 33.3%) and nausea (3 subjects, 25.0%). Three subjects (25.0%) had 5 adverse events that were grade 3 in severity (dehydration, edema, fatigue, urinary tract infection, and vomiting); no grade 3 adverse event preferred term was reported in > 1 subject.

Since AMG 404 doses up to [REDACTED] mg administered every 4 weeks have been shown to be tolerable, with the only treatment-related adverse event occurring in > 1 subject of nausea in 2 subjects (16.7%), the highest dose explored ([REDACTED] mg) will be used for combination therapy with AMG 596. If a higher AMG 404 dose will be declared as recommended phase 2 dose in the ongoing Phase 1 study (Study 20180143), such a

dose can be explored in additional cohort(s) in combination with AMG 596 whereby using the highest AMG 596 dose shown to be tolerated in the combination cohorts with AMG 404.

For AMG 596, the start dose in combination with AMG 404 treatment is based on the observation of pharmacodynamic effects observed at [REDACTED] µg/day in Group 1 subjects with recurrent malignant glioma. For Group 1 subjects, a dose of [REDACTED] µg/day administered in [REDACTED] infusion cycles will therefore be selected as first dose. The next AMG 596 pre-defined doses will be used for further dose escalation.

For Group 2 subjects, the starting dose of AMG 596 in combination with AMG 404 will be one dose level below the selected start dose for AMG 596 monotherapy (eg a start dose of [REDACTED] µg/day for AMG 596 monotherapy in Group 2 subjects leads to the selection of [REDACTED] µg/day as start dose for AMG 596 in combination with AMG 404 in Group 2 subjects). The next AMG 596 pre-defined doses will be used for further dose escalation.

To avoid cumulative toxicity associated with initial T cell activation after treatment start, a first dose of AMG 404 will not be given until [REDACTED] after start of the AMG 596 infusion. Prophylactic dexamethasone treatment as described in [Section 6.5](#), should be given before starting any AMG 596 infusion. Dose escalation will start with single subject cohorts as a pharmacodynamic effect is expected resulting in a reduced cytotoxic potency of AMG 596 when co-administered with dexamethasone.

2.6 Clinical Hypotheses

- AMG 596 monotherapy and in combination with AMG 404 are safe and well tolerated in at least one dose level when administered in subjects with EGFRvIII-positive glioblastoma or malignant glioma in the recurrent (Group 1) and in the maintenance setting (Group 2)
- AMG 596 monotherapy and/or in combination with AMG 404 can induce objective tumor shrinkage and/or overcome lack of response to standard of care (SoC) in subjects with EGFRvIII-positive glioblastoma or malignant glioma in either recurrent or in the maintenance setting at a tolerable dose

3. EXPERIMENTAL PLAN

3.1 Study Design

This is a first in human (FIH), open-label, sequential-dose-escalation study in subjects with EGFRvIII-positive glioblastoma or malignant glioma exploring AMG 596 monotherapy (Arm 1) and combination of AMG 596 with AMG 404 (Arm 2). Each arm of the study consists of 2 parts, dose escalation (Part 1) and dose expansion (Part 2). This

study will enroll 2 groups of subjects according to disease stage, recurrent disease (Group 1) and maintenance treatment after SoC in newly diagnosed disease (Group 2).

Part 1: Dose Escalation

The purpose of dose escalation is to make a preliminary estimate of the RP2D /MTD of AMG 596 monotherapy and in combination with AMG 404. Treatment is divided into 2 periods: (1) DLT period 1 for [REDACTED] of AMG 596 infusion and (2) DLT period 2 for [REDACTED] of AMG 596 infusion (applies for both Arms). This distinction between DLT period 1 and DLT period 2 is maintained throughout dose escalation until the end of the dose escalation phase. Observations from other BiTE® studies have shown that the occurrence of initial non-cumulative toxicities associated with cytokine release within first 48 hours after start of infusion may limit dose escalation below doses assumed to be associated with anti-tumor activity. However, should the initial dose (DLT period 1) be limited by severe adverse events related to first dose effects (eg, cytokine release associated adverse events) an MTD for the first dose step may be defined. Further dose escalation in DLT period 2 is possible resulting in a step-dosing and a second (and higher) MTD. This approach supports the ongoing evaluation of initial toxicity, as well as toxicity after an MTD for the start dose has been defined.

The AMG 596 start dose based on preclinical evaluations for the estimation of the MABEL is [REDACTED] µg/day. Further pre-specified nominal AMG 596 doses for potential use in any dose escalation Arm are [REDACTED] µg/day. The dose level review team (DLRT) may consider treating at intermediate doses if required. If the MTD or a biological active dose considered the RP2D is not reached within the pre-planned nominal dose range, the DLRT may decide to expand the nominal dose range to dose levels [REDACTED] µg/day after careful consideration of all available safety, laboratory, and PK information. The preliminary estimate of the RP2D/MTD of AMG 596 will be done initially in subjects with recurrent disease (Group 1) and separately in subjects with maintenance treatment after SoC in newly diagnosed disease (Group 2) and separately for AMG 596 monotherapy and in combination with AMG 404. If the same AMG 596 doses are to be explored in monotherapy and in combination, the monotherapy cohort must be completed before enrollment in the combination cohort. In the multiple subject cohorts, a safety observation window of at least 72 hours must apply between start of subjects 1, 2 and 3 of each dose escalation cohort. Intra-subject dose escalation will be allowed to higher AMG 596 dose levels in subsequent treatment cycles

Approved

once a higher dose has been deemed safe by the DLRT. Subjects who do not proceed to a higher dose may continue at the original dose.

Group 1, Recurrent Disease

- *Dose Escalation in single subject cohorts*
 - AMG 596 monotherapy: In first cohorts AMG 596 will be administered as a cIV infusion for [REDACTED] at escalating doses with N=1 per cohort. In the single subject cohorts, only a limited number of subjects will be enrolled at dose levels anticipated to be lower than those at which visible pharmacodynamics activity including adverse events related to AMG 596 therapy will be expected. In addition, the investigator together with the subject will decide on subsequent treatment duration carefully. Subjects are allowed to stay on study in [REDACTED] cycles until discontinuation criteria apply.
 - Combination of AMG 596 with AMG 404: The starting dose of AMG 596 is [REDACTED] µg/day administered in [REDACTED] cycles and the defined AMG 404 dose is [REDACTED] mg every 4 weeks.
 - The cohort size will be increased to N=2-4 subjects (= Start of multiple subject cohorts) after observation of
 - Treatment-related adverse events of common terminology criteria for adverse events (CTCAE 4.0) grade 2 or higher and/or
 - Quantifiable cytokine levels in blood or CSF above baseline
- *Dose Escalation in multiple subject cohorts:*
 - Subjects in the first multiple subject cohort receive the same dose as the last single subject cohort.
 - All subjects receive AMG 596 in [REDACTED] infusion cycles until treatment discontinuation criteria apply.

It is anticipated that dose-escalation will proceed according to the pre-planned nominal doses though intermediate dose levels may be used if required after reviewing all available safety data. When a first DLT is observed, the Bayesian logistic regression model (BLRM) will be used to guide dose level selection (Neuenschwander, Branson, & Gsponer, 2008). The cohort size will be N=2-4 subjects. On a limited basis, after agreement between the investigator and medical monitor, one additional subject may be allowed to be enrolled if the subject has been determined to be eligible and the cohort has been filled. In this case, all five subjects will be reviewed and assessed in the Dose Level Review Meeting (DLRM). After each cohort, the model's recommended MTD dose level for evaluation is the dose level with the highest probability of the target toxicity probability interval (TPI), but with a less than 0.25 probability of an excessive or unacceptable TPI. The target TPI is (0.20,

0.33], and TPIs of (0.33, 0.60] and (0.60, 1.00] are defined as excessive and unacceptable, respectively. The actual dose selected at each dose decision may be at or below the model's recommended dose as determined by the DLRT after considering all information. Dose escalation will be completed when any of the following occurs:

- The maximum total sample size of N=45 DLT evaluable subjects (including single subject cohorts) is reached for AMG 596 monotherapy or N=30 DLT evaluable subjects for AMG 596 in combination with AMG 404.
- The BLRM model recommends the same dose level at least 2 times and that at least 6 subjects have been treated at the recommended RP2D/MTD dose level. If step-dosing required, this stopping criterion applies separately to each period.
- The highest planned dose level is reached without any DLTs being observed

Group 2, Maintenance Treatment after SoC in Newly Diagnosed Disease

- A first cohort will start after observation of a first objective antitumor response in Group 1 subjects with recurrent EGFRvIII-positive glioblastomas or malignant glioma. The starting dose of AMG 596 monotherapy in Group 2 will be decided by DLRT and will be the current highest dose deemed safe of Group 1. Treatment may consist either of [REDACTED] dose AMG 596 cIV [REDACTED] or step-dosing as established for recurrent disease. Further treatment cycles with [REDACTED] between cIV infusions will be provided until any of the treatment discontinuation criteria apply.
- The starting dose of AMG 596 in combination with AMG 404 for Group 2 will be one dose level below the selected start dose for AMG 596 monotherapy and an AMG 404 dose of [REDACTED] mg.
- The BLRM will be used to guide dose level selection. The cohort size will be N=2-4 subjects. The actual dose selected at each dose decision may be at or below the model's recommended dose as determined by the DLRT after considering all information.
- Dose escalation in Group 2 will be completed when any of the following occurs:
 - The maximum sample size of N=15 DLT evaluable subjects is reached for AMG 596 monotherapy or N=20 DLT evaluable subjects for the AMG 596 in combination with AMG 404.
 - At least 6 subjects have been treated at the recommended RP2D/MTD dose level
 - The highest pre-specified nominal dose level is reached without any DLTs being observed

Part 2: Dose Expansion

The purpose of dose expansion will be to further explore safety and to evaluate preliminary antitumor-activity in subjects with recurrent disease (Group 1) and in

subjects with maintenance setting (Group 2). It is anticipated that 15 subjects will be enrolled to Group 1 in Arm 1 and Arm 2, respectively. Up to 25 subjects will be enrolled to Group 2 in Arm 1 and Arm 2, respectively.

In Group 2 both for Arm 1 and Arm 2, the objective response rate (ORR) of interest is 20% or higher while an ORR of 5% or less is considered insufficient antitumor-activity. For each arm, the ORR in Group 2 will be initially evaluated after 10 subjects are treated and have been evaluated at the first imaging scan or have dropped out before that. If ORR is lower than 5%, enrollment may be terminated due to futility. Otherwise, the ORR will be evaluated for additional new subjects and the futility stopping rules are calculated using a Bayesian predictive probability design (see [Section 10.2](#) for details).

[figure not shown]
During dose expansion and separately for the monotherapy arm (combining data from Groups 1 and 2) and for the combination arm (combining data from Groups 1 and 2), Amgen will conduct evaluations of the ongoing grade 4 or higher treatment-related adverse event rate to assess if the threshold for possible early trial termination has been reached. The threshold for holding enrollment is as follows.

| Number of subjects | Hold enrollment if observing this many grade 4 or higher treatment-related adverse events |
|--------------------|---|
| 10 | ≥ 4 |
| 20 | ≥ 6 |
| 30 | ≥ 9 |
| 40 | Study Complete |

If this threshold is met, enrollment to dose expansion will be halted pending review of safety data by the DLRT. After receiving the DLRT recommendation, Amgen will choose to take one of the following actions: 1) Terminate the trial 2) Amend the protocol to potentially improve the benefit/risk for subjects (eg, increase safety monitoring, modify dose/schedule, mandate premedication) 3) Continue dose expansion without any changes. See [Section 10.2](#) for further details regarding the derivation of these thresholds.

A BLRM design may be used to update the estimate of the RP2D/MTD using data from subjects enrolled to dose escalation and dose expansion. Based on this revised RP2D/MTD estimate and reviewing all available safety data, the dose level for dose expansion may be revised.

The subjects enrolled in Part 2 dose expansion will be followed by imaging evaluation until the earliest of: clinically significant disease progression, death, consent withdrawal, start of new anti-tumor therapies or 12 months after treatment initiation. Subjects who stopped treatment will be contacted for long term follow up for up to 12 months after treatment initiation.

Approved

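### The Group 2 combination start dose is fixed by a formula that rests on Group 1 monotherapy tolerability; nothing makes Group 1 combination DLT data a limit on it or says that they enter the BLRM for that first cohort

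*Protocol*

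**What the plan says.** The start-dose rule appears three times. Section 3.1 and the synopsis give it as in "The starting dose of AMG 596 in combination with AMG 404 for Group 2 will be one dose level below the selected start dose". Section 2.5.3.2 repeats it: "For Group 2 subjects, the starting dose of AMG 596 in combination with AMG 404 will be one dose level below". The Figure 1 note, as reproduced in the Amendment 5 description of changes, says the same.

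The anchor is the Group 2 monotherapy start dose. Section 3.1 leaves it to the DLRT and sets it at the current highest Group 1 dose judged safe. Section 2.5.3.1 makes clear that this is a monotherapy dose: Group 2 escalation "can start at the highest AMG 596 monotherapy dose deemed to be tolerated by DLRT for Group 1 subjects".

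Group 2 opens on a first objective response in Group 1 (3.1, 5.1). The Amendment 5 rationale reports that such a response had already been seen on monotherapy. If the same AMG 596 dose is used in both arms, the monotherapy cohort must finish first. At different doses the arms may run in parallel (5.1).

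On combination risk, 2.5.3.2 states that no clinical safety information exists and that "adverse events caused by synergistic activation of T cells are expected".

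For later dosing, 3.1 has the BLRM guide Group 2 and lets the DLRT choose at or below the model's "recommended dose as determined by the DLRT after considering all information". The numerical overdose limit, "but with a less than 0.25 probability of an excessive or unacceptable TPI", is written in 3.1 under Group 1. Section 10.3 describes overdose control for both arms, and the SAP's MTD definition (Section 5) gives the 0.25 limit without naming a group.

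**The concern.** The sentence that sets this dose says what it will be, and its inputs are all monotherapy inputs. Group 1 Arm 2 could have produced DLTs at or near the formula dose, or no data at all, and the formula would give the same answer. Group 2 cohorts have 2 to 4 subjects, so several people could receive a combination dose that is untested, or was poorly tolerated, in Group 1 Arm 2.

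The model would be the natural check, but its inputs for this cohort are not stated. If it uses Group 2 data only, it holds no DLT data when the cohort opens and rests on the prior alone. Elsewhere the protocol does state such links. The expansion safety rule pools the groups, separately for monotherapy "and for the combination arm (combining data from Groups 1 and 2), Amgen will conduct evaluations". A higher AMG 404 dose would be explored "using the highest AMG 596 dose shown to be tolerated in the combination cohorts with AMG 404". This start dose has no such sentence.

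**Working it through.** **1. What the text requires.** Each element that sets or opens the first Group 2 Arm 2 cohort, and whether it uses Group 1 Arm 2 data:

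| Element | Source | Group 1 Arm 2 data required? |
|---|---|---|
| One level below the monotherapy start | 3.1, synopsis, 2.5.3.2 | No |
| Monotherapy anchor | 3.1, 2.5.3.1 | No |
| Opening trigger (first Group 1 response) | 3.1, 5.1 | No |
| Monotherapy first at the same dose | 3.1, 5.1 | No |
| BLRM guidance | 3.1, 10.3 | Inputs not stated |
| DLRT review of all study data | 10.4.2 | Reviewed, not a limit |

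Sections 10.4.1 and 10.5.2 establish the RP2D/MTD separately by group and summarize BLRM results by dose and group. That leans towards group-specific models without saying so.

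**2. The plan's own figures.** No figure is attached to this rule. The nearest is the chance of at least one DLT in a cohort (10.2), 1 − (1 − p)^n. For n = 2 it is 0.190 at p = 0.10 and 0.556 at p = 1/3. For n = 6 it is 0.469 and 0.912. These match the stated 19-56% and 47-91%.

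**3. Could the unstated input matter?** An illustration with the 10.3 model. The assumptions are that 0.05 and 0.25 are prior medians at the lowest and reference doses, and that the unstated prior correlation lies between −0.7 and 0.

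- Reference dose: log a is normal with mean logit 0.25 = −1.099 and sd (logit 0.25 − logit 0.05)/1.645 = (−1.099 + 2.944)/1.645 = 1.122. This gives P(p ≤ 0.05) = 0.05, as 10.3 states.
- Slope: X = b·log(d_ref/d_min) is lognormal, fitted so that at the lowest dose the median is 0.05 and P(p ≤ 0.40) = 0.90. Mean and sd of log X by correlation: −0.7 (0.572, 0.934); −0.5 (0.529, 1.180); −0.3 (0.467, 1.588); 0 (0.279, 3.157).
- Then logit p(t) = log a − X(1 − t), where t is the relative log dose (0 lowest, 1 reference). The redacted doses enter only through t.

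P(DLT rate > 0.33) with a binomial likelihood, range over the correlations, against the limit of 0.25:

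| Group 1 Arm 2 data at the start dose | t = 0 | 0.25 | 0.5 | 0.75 | 1 |
|---|---|---|---|---|---|
| not in model | 0.14 | 0.15-0.16 | 0.17-0.20 | 0.20-0.26 | 0.36 |
| 1/4 DLTs | 0.19-0.21 | 0.20-0.22 | 0.22 | 0.23-0.24 | 0.29 |
| 2/4 DLTs | 0.52-0.53 | 0.53 | 0.53-0.55 | 0.54-0.57 | 0.60 |

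Over all five points, 0/2 gives 0.04-0.18 and 0/4 gives 0.02-0.09.

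If the data lie one level below the start dose (a level being 1/6 to 1/3 of the range, start dose at the midpoint or higher), 2/4 gives 0.56-0.76 and 1/4 gives 0.24-0.44.

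In the lower half of the range, then, the same dose passes with Group 1 Arm 2 data left out and fails with 2/4 included. With 0/2, 0/4 or 1/4 at that dose it passes either way. At the reference dose it fails on the prior alone, and there 0/2 would bring it under the limit. Including the data can therefore relax the decision as well as tighten it.

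**The case against.** The protection in place is considerable. The DLRT must review all available study data and can de-escalate, delay or stop (10.4.2), so Group 1 combination DLTs would be before the people who decide. The BLRM guides Group 2 with no wait for a first DLT, and the DLRT may go lower. Overdose control in 10.3 covers both arms with no group restriction. Monotherapy at the same dose comes first. The one-level step-down is itself a margin for the combination. AMG 404 is delayed after the start of AMG 596 (2.5.3.2), and dexamethasone prophylaxis is mandatory (6.2.1.1, 6.5). Harm would need a DLRT that had seen something like 2/4 combination DLTs and still opened that dose. Group-specific models would also be a legitimate choice, since 2.5.1 assumes that subjects with lower disease burden may tolerate more.

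Most of this stands, and it rules out stronger readings. A reader might infer that Group 2 Arm 2 has no overdose control. Section 10.3 and the SAP's MTD definition do not support that, although the SAP predates Arm 2 and defines an MTD rather than a start dose. A reader might infer that the models are group-specific. Sections 10.4.1 and 10.5.2 speak of estimates and reporting, not of model inputs. A reader might also infer that the formula dose will exceed what Group 1 Arm 2 tolerated. With doses redacted, that is unknown.

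What the objection does not supply is a sentence that makes combination data a limit. The safeguards are permissive, and the combination start-dose sentence does not mention the DLRT, whereas the monotherapy sentence before it does.

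**Conclusion.** The point holds as a gap in a binding rule, and a modest one. The Group 2 Arm 2 start dose is fixed from monotherapy tolerability, no combination data are required to set or open it, and the role of Group 1 Arm 2 DLTs in the model for that cohort is unstated. A careful DLRT could reach the right dose under the present text, so this is an inexpensive improvement and not a demonstrated design fault.

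The textual finding does not depend on the redacted doses. The size does. The contrast between at most 0.20 and at least 0.52 rests on an assumed dose position, the reading of the prior anchors as medians, an assumed correlation range and 2/4 DLTs at the same dose.

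**What to change.** In 3.1, the synopsis, 2.5.3.2 and the Figure 1 note, let the DLRT decide and turn the formula into a ceiling. Suggested wording: *will be decided by the DLRT, will be no higher than one dose level below the Group 2 monotherapy start dose, and must meet the <0.25 overdose criterion in a BLRM that includes all available Arm 2 DLT data (Group 1 included).* Add that if no Group 1 Arm 2 cohort has completed its DLT period, Group 2 Arm 2 starts no higher than the Group 1 Arm 2 start dose.

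This applies to the first cohort only. Later Group 2 escalation and the separate RP2D/MTD estimation stay as they are. No further cap is needed, because the 0.25 criterion is already defined.

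The cost is wording in three sections and one figure note, plus one BLRM run on data the trial already collects. Group 2 Arm 2 may start lower or slightly later, but it need not wait for a cleared Group 1 Arm 2 dose.
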